8.4 DATA SOURCES

8.4.1 Collection of Data on the electronic CRF (eCRF)

Patients' data will be recorded on electronic case report forms (eCRFs). The degree of detail and completeness of data collected is dependent on local clinical practice. Data from patient notes should be entered on the eCRF as soon as they become available.

8.4.2 Data Collected during the Observation Period

During therapy with ocrelizumab, laboratory assessments are expected to be routinely performed in accordance with current guidelines and local standard of care. In the routine care setting, patients are seen regularly by their treating physicians either for treatment or for regular assessments after treatment. When performed during the observational period, available results from the range of assessments described below will be documented on the eCRF. Most data will be documented at baseline and approximately every six months according to standard of care. The proposed assessments and suggested timings for assessments in the protocol/observational plan are not mandatory. It is up to the treating physician to perform and document the assessments as performed in the real clinical setting.

All AEs occurring during the observational period will be reported. In addition, laboratory parameters (blood cell count, immunoglobulins, liver enzymes, and renal status), vital signs and weight will be recorded as available at baseline and every six months.

Effectiveness of treatment will be assessed via MS specific symptoms, relapses, and Expanded Disability Status Scale (EDSS) at baseline and approximately every six months and via MRI if available. Patient reported outcomes (PRO) regarding quality of life (QoL) and pharmacoeconomic outcomes will be collected at baseline and every six months or less frequently via questionnaires. Although the completion of such questionnaires is not routine practice it is allowed according to local regulations.

The following data will be collected during the study, as part of the local routine clinical practice:

Baseline (Study enrollment):

- Documentation of written informed consent
- Patient demographic information,
- Weight and height
- Medical history and comorbidities (including significant medical and surgical history, previous malignancies and precancerous lesions)
- Vital signs (blood pressure [BP], heart rate [HR], body temperature)

- Ocrelizumab administration information (e.g., start date, dose, dosing frequency)
- Any malignancy risk factor information available:
 - Tobacco use history
 - Alcohol use history
 - Family disease history, including genetic testing (e.g. BRCA1 and 2), if available
 - Personal history of malignancy
 - Other risk factors (e.g., obesity, metabolic syndrome, radiation exposure, hormone replacement therapy exposure, reproductive history, immunosuppression, infection known to be associated with an increased risk of malignancy, etc.)
- MS disease and treatment history
 - Date of MS symptoms onset and date of MS diagnosis
 - Type of MS
 - MS relapse history
 - All previous treatments and therapies for MS, including their duration (start/stop dates)
 - All other prior and concomitant immunomodulatory and immunosuppressive treatments including their duration (start/stop dates)
 - MS status at initiation with ocrelizumab, including most recent Expanded Disability Status Scale (EDSS) score, if available
- Any other prior and concomitant medications from 3 months prior to enrollment
- Pregnancy status, if applicable (patient-reported, female patients)
- · Laboratory parameters, if available:
 - Blood cell count (red blood cell count [RBC], hemoglobin, hematocrit, absolute and differential white blood cell count [WBC], absolute neutrophil count [ANC], quantitative platelet count)
 - o Immnunoglobuline levels (IgG, IgM, IgA)
 - Liver enzymes (alanine transaminase [ALT], aspartate transaminase [AST], gamma-glutamyl transpeptidase [gamma-GT])
 - o Renal status (creatinine, blood urea nitrogen [BUN], urinalysis)
 - Clinical chemistry (alkaline phosphatase, amylase, total bilirubin, urea, uric acid, random glucose, potassium, sodium)
 - Flow cytometry (B-cell depletion and recovery [CD19+] and T-cell counts [CD3+, CD4+, CD8+])
 - Viral serology and detection (Hepatitis B, Hepatitis C, HIV)
- QoL / PRO:

- o Clinical Global Impression (CGI)
- o Treatment Satisfaction Questionnaire for Medication (TSQM1.4)
- Multiple Sclerosis Impact Scale (MSIS-29 v2)
- Symbol Digit Modality Test (SDMT)
- Clinical management questions:
 - o Gynecological consultation
 - Breast check
 - o Dermatological check
- Malignancy/cancer detection tests (e.g., mammography, Pap test, colonoscopy, laboratory malignancy markers)
- Pharmacoeconomic outcomes:
 - Work Productivity and Activity Impairment Questionnaire: Multiple Sclerosis (WPAI:MS)
- JCV antibody status / index
- Most recent MRI results, if available

Follow-up after study enrollment (anticipated every ~6 months):

- · Vital signs (BP, HR, body temperature) and weight
- Laboratory parameters, if available:
 - Blood cell count (RBC, hemoglobin, hematocrit, absolute and differential WBC, ANC, quantitative platelet count)
 - o Immunoglobuline levels (IgG, IgM, IgA)
 - o Liver enzymes (ALT, AST, gamma-GT
 - o Renal status (creatinine, BUN, urinalysis)
 - Clinical chemistry (alkaline phosphatase, amylase, total bilirubin, urea, uric acid, random glucose, potassium, sodium)
 - Flow cytometry (B-cell depletion and recovery [CD19+] and T-cell counts [CD3+, CD4+, CD8+])
- · Continuation of therapy or reason for discontinuation, if applicable
- Concomitant medications
- MS specific symptoms and treatment, relapses:
 - MS relapse during the treatment period (start/end dates)
 - Most recent EDSS score since the last encounter, if available
 - Most recent MRI results since the last encounter, if available
 - MS treatment changes and rationale

- Clinical management questions during study:
 - Gynecological consultation
 - o Breast check
 - Dermatological check
 - Malignancy/cancer detection tests (e.g., mammography, Pap test, colonoscopy, laboratory malignancy markers)
- Pregnancy status, if applicable (patient-reported, female patients)
- Safety assessments:
 - all AEs
 - SAEs
 - pregnancies
 - any malignancies, including but not limited to MedDRA Standardized MedDRA Queries (SMQ) of malignant or unspecified tumors, and non-melanoma skin cancers (NMSCs)
- Malignancy information, if applicable (questionnaire regarding in-depth malignancy information will be solicited from the patient's treating physician or oncologist [only collected if a malignancy is identified]), including, but not limited to:
 - Cancer type
 - Diagnosis date
 - Location of primary tumor
 - o Tumor grade
 - Stage at diagnosis
 - Action taken with ocrelizumab therapy at the point of diagnosis
 - AEs of special interest (AESIs):
 - Cases of potential medicine-induced liver injury that include an elevated ALT or AST in combination with either an elevated bilirubin or clinical jaundice, as defined by Hy's law (see Appendix 3).
 - Suspected transmission of an infectious agent by the study medicine (STIAMP)
 - Death information, if applicable (e.g., date of death, primary and underlying causes of death as entered for the AE)
- Ocrelizumab administration information (e.g., dates of administration [stop and restart dates, if applicable], dose, dosing frequency)
- QoL / PRO:
 - Clinical Global Impression (CGI)
 - Treatment Satisfaction Questionnaire for Medication (TSQM1.4)

- o Multiple Sclerosis Impact Scale (MSIS-29 v2)
- Symbol Digit Modality Test (SDMT)
- Pharmacoeconomic outcomes:
 - Work Productivity and Activity Impairment Questionnaire: Multiple Sclerosis (WPAI:MS)
- MRI, if available

At time of study completion or withdrawal from the study, if applicable:

- Ocrelizumab administration information (e.g., dates of administration [stop and restart dates, if applicable], dose, dosing frequency, reason for discontinuation)
- Vital signs (BP, HR, body temperature)
- Laboratory parameters:
 - Blood cell count (RBC, hemoglobin, hematocrit, absolute and differential WBC, ANC, quantitative platelet count)
 - o Immunoglobuline levels (IgG, IgM, IgA)
 - Liver enzymes (ALT, AST, gamma-GT)
 - o Renal status (creatinine, BUN, unrinalysis)
 - Clinical chemistry (alkaline phosphatase, amylase, total bilirubin, urea, uric acid, random glucose, potassium, sodium)
 - Flow cytometry (B-cell depletion and recovery [CD19+] and T-cell counts [CD3+, CD4+, CD8+])
- Concomitant medications
- MS specific symptoms and treatment, relapses:
 - MS relapse during the treatment period (start/end dates)
 - o Most recent EDSS score since the last encounter, if available
 - Most recent MRI results since the last encounter, if available
 - MS treatment changes and rationale
- Clinical management questions during study:
 - Gynecological consultation
 - o Breast check
 - Dermatological check
 - Malignancy/cancer detection tests (e.g., mammography, Pap test, colonoscopy, laboratory malignancy markers)
- Pregnancy status, if applicable (patient-reported, female patients)
- QoL / PRO:
 - Clinical Global Impression (CGI)

- Treatment Satisfaction Questionnaire for Medication (TSQM1.4)
- o Multiple Sclerosis Impact Scale (MSIS-29 v2)
- Symbol Digit Modality Test (SDMT)
- Pharmacoeconomic outcomes:
 - Work Productivity and Activity Impairment Questionnaire: Multiple Sclerosis (WPAI:MS)
- Safety assessments:
 - all AEs
 - SAEs
 - pregnancies
 - any malignancies, including but not limited to MedDRA SMQ of malignant or unspecified tumors, and NMSCs
 - Malignancy information, if applicable (questionnaire regarding in-depth malignancy information will be solicited from the patient's oncologist [only collected if a malignancy is identified]), including, but not limited to:
 - o Cancer type
 - o Diagnosis date
 - Location of primary tumor
 - Tumor grade
 - Stage at diagnosis
 - Action taken with ocrelizumab therapy at the point of diagnosis
 - · AESIs (i.e., Hy's Law and STIAMP only)
 - Death information, if applicable (e.g., date of death, primary and underlying causes of death as entered for the AE)
- Reason for study withdrawal

Scheduled assessments for the study are presented in Table 1 below.

 Table 1
 Data Collection Overview (as per Standard of Care)

ie 1 Data Collection Overview (as p	er Stariuaru bi	Care	
Data Collection ^a	Baseline ^b (Study Enrollment)	Data Collected every ~6 months	Data Collected at Study Completion/ Early Termination Visit
Informed consent ^c	Х		
Inclusion/exclusion criteria	Х		
Patient demographics, height and weight	х		
MS disease history ^d	Х		
MS treatment history ^e	х		
Medical history and comorbidities f	Х		
Malignancy risk factor information ^g	Х		
JCV antibody status / index	Х		
Prior and Concomitant medications h	Х	Х	х
Ocrelizumab administration information i	х	Х	х
Vital signs	Х	Х	х
MS specific symptoms and treatment, relapses ^j		х	х
Clinical management k	Х	Х	х
Laboratory parameters ^I	Х	Х	х
Pregnancy status ^m	Х	Х	х
QoL / PRO ⁿ	Х	Х	х
Pharmacoeconomic outcomes °	Х	Х	х
MRI	Х	Х	х
All serious and non-serious AEs incl. AESIs and information on reasons for death, if applicable	whenever occur		
Pregnancies ^p	whenever occur during treatment with ocrelizumab and within 6 months after last administration		
Any malignancies (incl. NMSCs) and malignancy-specific questionnaire q, s	whenever occur		
Continuation of therapy or Reasons for treatment discontinuation ^{r, s}		х	х
Premature termination incl. reasons for withdrawal ^s		Х	х

AE: adverse event; AESI: adverse event of special interest; MRI: magnetic resonance imaging; MS: multiple sclerosis; NMSC: non-melanoma skin cancer; SAE: serious adverse event; PRO: patient reported outcome; QoL: quality of life; STIAMP: suspected transmission of infection by a medicinal product

- Available data will be collected; no additional diagnostic or monitoring procedures shall be applied to the patients outside of routine clinical practice
- b Up to 30 days prior to first ocrelizumab infusion
- Written informed consent must be obtained before any data collection (per local regulations or ethics committee requirements)
- Including MS date of diagnosis, type of MS, duration of MS, MS disease symptom history, relapse history, EDSS and MRI results (if available)
- Prior use and duration of therapies for MS and prior use and duration of immunomodulatory, immunosuppressive, and anti-neoplastic agents (if any)
- f Including significant medical and surgical history, previous malignancies and precancerous lesions
- Including tobacco use history, alcohol use history, family disease history (e.g., genetic testing such as BRCA1 and 2), personal history of malignancy, or other risk factors
- ⁿ Up to 3 months prior to enrollment
- Dates of administration (start, stop, and restart dates), dose, dosing frequency, reason for discontinuation (if applicable)
- Including MS relapse during treatment period, MS type changes, date of last administration of ocrelizumab (if applicable), MS treatment changes and rationale, most recent EDSS score since last encounter (if available), most recent MRI results since last encounter (if available)
- Including gynecological consultation, breast check, dermatological check, or other malignancy/cancer detection tests (e.g., mammography, Pap test, colonoscopy, laboratory malignancy markers)
- Blood cell count, immunoglobulins, liver enzymes, renal status, clinical chemistry, flow cytometry, viral serology
- Patient-reported, female patients
- ⁿ TSQM1.4, MSIS-29v2, CGI, SDMT. Collected every six months
- WPAI:MS. Collected every six months
- P AESIs are Hy's Law and STIAMP only
- ^q Questionnaire regarding in-depth malignancy information will be solicited from the patient's oncologist (only collected if a malignancy is identified)
- Including number of attempts to contact patient, method of contact, and reasons for early termination (e.g., death, withdrawal of consent, lost to follow-up)
- s If applicable

All assessments will be performed per standard of care (SoC). There are no mandated study visits, and data from any encounter with the neurologist during follow-up will be entered by clinicians (anticipated to occur every ~6 months). Follow-up is planned regardless of whether patients discontinue treatment with ocrelizumab. Please see Table 1 in section 8.4.2 for the data collection overview (as per standard of care with exception of questionnaires) during the treatment period.

8.4.3 Data Collected at Study Completion

All patients treated with at least one dose of ocrelizumab will be observed for the whole period of at least 7.5 and up to 10 years, regardless whether ocrelizumab treatment is discontinued during the course of the study. For patients who complete this observation

period either as scheduled or due to withdrawal, the study completion visit should be documented. Study completion encounter assessments should be completed if possible.

Please see Table 1 in section 8.4.2 for the data collection overview at the study completion visit, if available.

8.4.4 Safety Data Collection

Clinical AEs, serious and non-serious, as well as safety data other than AEs as described in Section 8.3 will be recorded in the eCRF during the observation period. For clinical AEs, serious and non-serious, physician's assessment of severity (according to Common Terminology Criteria for Adverse Events [CTCAE]) and relationship to therapy (i.e., related or unrelated) will be recorded as described in Appendix 3. Every CTCAE Grade 4 has to be reported as an SAE.

A pregnancy has to be reported as an AE within the eCRF.

AEs which are symptoms of the MS and expected during the course of the disease are not to be recorded in the eCRF.

Medical occurrences or symptoms of deterioration that are anticipated as part of MS or which are expected in the patient population studied should be recorded as an AE only if judged by the physician to have unexpectedly worsened in severity or frequency or changed in nature at any time during the study.

Following the above rationale, all events that are captured in scope of the effectiveness objective, will not be considered as Adverse Events for this study:

- Hospitalizations following an MS relapse as long as the reason for hospitalization is to receive standard treatment with i.v. methylprednisolone, is not considered as SAE
- EDSS progression
- MRI activity (new T2 or Gadolinium enhancing lesion in spinal or cerebral MRI)MS signs and symptoms
- Disability
- events originating from patient questionnaires (e.g. fatigue, pain, cognition decline)

As health-related quality of life is a secondary endpoint of this study all MS-related AEs reported within the patient-reported outcome using the Treatment Satisfaction Questionnaire for Medication (TSQM1.4), Multiple Sclerosis Impact Scale (MSIS-29 v2), Clinical Global Impression (CGI), and Symbol Digit Modality Test (SDMT) should not be

documented per default within the eCRF. During site review of the PRO questionnaire data the physician/study personnel should screen for additional potential safety information out of scope of the questionnaires. If the criteria for an adverse event have been met this must be reported using the Adverse Event eCRF, if not already documented.

As the Pharmacoeconomic outcome 'Work Productivity and Activity Impairment Questionnaire: Multiple Sclerosis (WPAI:MS)' is an exploratory endpoint of this study all AEs reported within the scope of the questionnaire should not be documented per default within the eCRF, but only if not MS-related AEs have been added by the patient .

Abnormal laboratory parameters i.e. blood cell count (RBC, hemoglobin, hematocrit, WBC, platelets), immunoglobulins, liver enzymes (ALT, AST, gamma-GT), renal status (creatinine, BUN, unrinalysis), clinical chemistry, flow cytometry, viral serology should be only recorded in the eCRF as an AE when the treating physician considers the deviating laboratory parameters as medically significant.

8.5 STUDY SIZE

The primary objective of this study is to investigate the occurrence of uncommon adverse events in multiple sclerosis patients receiving treatment with ocrelizumab over a maximum time period of 10 years. The sample size is thus planned to allow for the detection of adverse events with an incidence rate of at least 0.1% (1 out of 1000 patients) at least once with a probability of 95%. Applying the Poisson distribution model for uncommon events, this results in a total sample size of approximately 3000 patients. Taking into account that ocrelizumab is currently the only approved disease modifying medication for PPMS and the resulting unmet need in this population approximately 700-1000 are expected to be PPMS patients. Patient recruitment and observation will take place at approximately 250 centers.

With the sample size of 3000 patients in this non-interventional study (NIS), following precision of the estimation of incidence rates in terms of 95% confidence intervals (Clopper-Pearson) can be obtained:

Table 2 95% Confidence Intervals for the Primary Safety Outcome Measures Based on 3000 Patients Receiving Ocrelizumab

Number of AE events/observed AE incidence	95% Confidence Interval (Clopper-Pearson) for the incidence rate
3 (0.1%)	[0.02%; 0.29%]
15 (0.5%)	[0.28%; 0.82%]
30 (1.0%)	[0.68%; 1.42%]

8.6 DATA MANAGEMENT

8.6.1 Data Quality Assurance

A CRO will be responsible for data management of this study, including quality checking of the data. All data will be collected via electronic data capture (EDC). Sites will be responsible for data entry into the EDC system. In the event of discrepant data, the CRO will request data clarification from the sites, which the sites will resolve electronically in the EDC system.

A Data Quality Review Plan will be produced that describes the quality check to be performed on the data.

Roche will perform oversight of the data management of this study, including approval of the CRO data management plans (including Data Quality Review Plan) and guidance. Data will be periodically transferred electronically from the CRO to Roche, and the CRO's standard procedures will be used to handle and process the electronic transfer of these data.

eCRFs and correction documentation will be maintained in the EDC system audit trail. System backups for data stored at MedicalSyn and records retention for the study data will be consistent with MedicalSyns standard procedures. MedicalSyn will comply with the Roche's procedures regarding archiving and record management.

8.6.2 Electronic Case Report Forms

eCRFs are to be completed using a Roche-approved EDC system. Sites will receive training and have access to a manual for appropriate eCRF completion. eCRFs will be submitted electronically to CRO and should be handled in accordance with instructions from CRO.

All eCRFs should be completed by designated trained site staff. eCRFs should be reviewed and electronically signed and dated by the physician or a designee.

At the end of the study, the physician will receive the data related to patients from his or her site in an electronically readable format (e.g., on a compact disc). Data must be kept with the study records. Acknowledgement of receipt of the data is required.

8.6.3 Source Data Documentation

Site Operations Representative will perform ongoing source data verification (SDV) as defined in the Trial Monitoring Plan to confirm that critical protocol data (i.e., source data) entered in the eCRF by authorized site personnel are accurate, complete, and verifiable from source documents.

Source documents (paper or electronic) are those in which patient data are recorded and documented for the first time. They include, but are not limited to, hospital records, clinical and office charts, laboratory notes, memoranda, PROs, evaluation checklists,

pharmacy dispensing records, recorded data from automated instruments, copies of transcriptions that are certified after verification as being accurate and complete, microfiche, photographic negatives, microfilm or magnetic media, X-rays, patient files, and records kept at pharmacies, laboratories, and medico-technical departments involved in a clinical study.

Before study initiation, the types of source documents that contain study-relevant information will be clearly defined in the Trial Monitoring Plan. The Trial Monitoring Plan defines which kind of source data – if available from routine clinical practice - can be used for documentation into the eCRF. No additional source data creation beyond routine is allowed.

Source documents that are required to verify the validity and completeness of data entered in the eCRF must not be obliterated or destroyed and must be retained per the policy for retention of records described in Section 8.6.5.

To facilitate SDV, the physicians and institutions must provide Roche direct access to applicable source documents and reports for study-related monitoring, Roche audits, and EC review. The participating sites must also allow inspection by applicable health authorities.

8.7 DATA ANALYSIS

The statistical analysis will be described in a prospective statistical analysis plan. This plan will summarize all analyses in detail. Statistical analysis will be mainly based on descriptive methods. To check for potential channeling effects various time spans of patients enrolled will be analyzed. No hypothesis testing will be performed in this NIS. All analyses are regarded exploratory in nature.

All available data will be included in the analyses and will be summarized as far as possible. In general, there will be no substitution of missing data, i.e. missing data will not be replaced, missing data will be handled as 'missing' in the statistical evaluation ('observed cases analysis'). All data of patients who withdraw (e.g., who discontinued prematurely) will be documented anonymously and discussed, as necessary, in the clinical study report.

Generally, all safety analyses will be presented separately for the MS types RMS and PPMS patients as well as pooled. Analyses of effectiveness will be prepared by MS type only.

8.7.1 Safety Analyses

Analysis population

The core analysis population consists of all enrolled patients with data available.

The following analysis sets of patients will be used in this study:

- Enrolled Set (ES) defined as all patients recorded in the clinical database
- Safety Set (SS) defined as all patients in the ES treated with at least one dose of studied medicinal product
- Full Analysis Set (FAS) defined as all patients of the SS who had at least one documentation after start of the therapy

The safety analyses will be done for the safety analysis population, the effectiveness analyses will be done for the Full Analysis Set. All other analyses will be done for all enrolled patients.

Handling of deviations from the study protocol will be detailed in the SAP or a separate document. It is planned to organize a Data Review Meeting prior to database hard lock and database freeze for interim analyses. This preanalysis review should cover decisions concerning the exclusions of patients or data from the analysis sets.

Patient Disposition

Tables for disposition will be provided for the ES. A flowchart will show the final disposition of all patients in the different analysis sets according to the treatment cohorts together with a summary of the reasons for exclusion.

Baseline Characteristics and demographics

Characterization based on relevant baseline data (age, PPMS history, status at start of PPMS treatment) will be performed by means of descriptive statistics for continuous data or frequency tables for categorical data. Previous and concomitant diseases will be coded and presented according to the MedDRA terminology. Summary tables will be provided for the SS and the FAS.

Analysis of primary endpoint

The analysis of the primary endpoint will be done on the safety analysis population. Incidence rates of adverse events will be calculated on the basis of system organ class and preferred term of the Medical Dictionary for Regulatory Activities (MedDRA) and presented along with two-sided 95% confidence intervals (Clopper-Pearson). In addition time adjusted analyses will be done based on patient years.

The analysis of safety outcomes/variables is based on the incidence and severity (NCI CTCAE grading) of all AEs and SAEs reported.

Events rates per 100 patient years (of treatment exposure) will be determined along with corresponding 95% confidence intervals.

Other safety analyses

Other safety endpoints will be analyzed descriptively in a similar fashion.

Selected lab outcomes/variables will be presented graphically, e.g. boxplots of the median, interquartile range, extreme values and outliers over time or mean and additional corresponding confidence intervals over time, based on standard units (SI units).

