8. RESEARCH METHODS

8.1 STUDY DESIGN

CONFIDENCE is a prospective, multicenter, non-interventional, long-term study collecting primary data in RMS and PPMS patients newly treated with ocrelizumab in routine clinical practice. To provide robust evidence on the safety and effectiveness profile of ocrelizumab in real-world conditions, data from 3000 MS patients from approximately 250 neurological centers and practices in Germany are planned to be included. At least 60% of the study population will be females. According to routine practice and as recommended by the German Society of Neurology (DGN Guideline 2015), visits are expected to be documented every 6 months in the main study period up to 10 years, after the initial infusions have been administered to the patient.

CONFIDENCE comprises an initial recruitment period of 30 months – which is anticipated to start in the first quarter 2018 – and will be followed by an observation period. Depending on the time point of study inclusion (i.e. start of ocrelizumab) each patient will be observed for a total duration of at least 7.5 and up to 10 years maximum, or until death / withdrawal of consent / loss to follow-up. Follow-up during the whole period is planned for all study participants, regardless of whether patients discontinue treatment with ocrelizumab or have a malignancy diagnosis. Data from CONFIDENCE will also be included in two global PAS studies (BA39730 & BA39731).

Study Flow

2000-2300 RMS patients and 700-1000 PPMS patients included in approx. 250 sites; first ocrelizumab infusion

Data collected: Informed consent, in-/exclusion criteria, patient demographics, MS disease history, MS treatment history, medical history and comorbidities, malignancy risk factor information, prior and concomitant medications, ocrelizumab administration information, vital signs, MS specific symptoms and relapses, clinical management, laboratory parameters, pregnancy status, QoL/PRO, pharmacoeconomic outcomes, JCV antibody status/index, MRI

Every ~6 months for at least 90 months (up to 10 years maximum)

Data collected: Ocrelizumab administration information, concomitant medication, AEs/SAEs/AESIs, vital signs, QoL/PRO, pharmacoeconomic outcomes, MRI, MS specific symptoms and relapse, laboratory parameters, pregnancy status, clinical management, follow-up on malignancies, treatment continuation/reasons for discontinuation (if applicable)

Study completion / Early termination visit

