10.1.2.1 Adverse Event Reporting Period

Physicians will seek information on AEs at each patient contact. All AEs subject to the collecting and reporting requirements outlined in this protocol, whether reported by the patient or noted by study personnel, will be recorded in the patient's medical record and in the AE section of the eCRF.

Once the patient is enrolled in the study, AEs will be collected until the end of his or her observation period. After this period, the physician is not required to actively monitor patients for AEs but if the treating physician becomes aware of any related AEs to any medicinal product they should be notified to the competent authority in the Member State where the reactions occurred or to the marketing authorization holder of the suspected medicinal product, but not to both (to avoid duplicate reporting).

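### Section 8.7.1, read literally, divides events from the whole observation period by ocrelizumab-exposure time only, so the patient-year rates come out too high

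*Protocol*

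**What the plan says.** Three parts of the protocol bear on this point.

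- **What is analysed.** Section 8.7.1: "The analysis of safety outcomes/variables is based on the incidence and severity (NCI CTCAE grading) of all AEs and SAEs reported".
- **What it is divided by.** The next sentence of Section 8.7.1: "Events rates per 100 patient years (of treatment exposure) will be determined along with corresponding 95% confidence intervals". Treatment exposure is not defined further. A preceding sentence also promises time-adjusted analyses by patient-years, without saying which time is meant.
- **How long events are collected.** Section 8.1: "each patient will be observed for a total duration of at least 7.5 and up to 10 years maximum", and "Follow-up during the whole period is planned for all study participants, regardless of whether patients discontinue treatment with ocrelizumab or have a malignancy diagnosis". Section 8.4.3 repeats that observation continues "regardless whether ocrelizumab treatment is discontinued during the course of the study". Section 10.1.2.1: "Once the patient is enrolled in the study, AEs will be collected until the end of his or her observation period".

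In Table 1 (Section 8.4.2), AEs, causes of death and malignancies are recorded whenever they occur. Only the pregnancy row has a window tied to treatment (on ocrelizumab or within 6 months of the last administration). Section 8.7.1 adds that the other safety endpoints are handled in a similar way. According to Section 8.3.2 these include serious infections, malignancies and malignancy mortality. Death is part of the primary outcome (Section 8.3.1).

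**The concern.** An incidence rate is interpretable when the events in the numerator arise from the time in the denominator. Here the numerator, as described, covers the patient's whole observation, while the denominator covers only the part spent on ocrelizumab. A patient who stops in year 3 and is diagnosed with a malignancy in year 7 adds one event but none of the four intervening years. The result estimates neither the rate while on treatment nor the rate among patients ever exposed.

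Malignancies and deaths are the most exposed to this, because both can occur long after stopping. They are also central to the study: Section 3 gives long-term data on malignancies and serious infections as a reason for doing it, and Sections 3 and 6.2 describe an unresolved imbalance in malignancies. The gap between observed and exposed time widens with follow-up. Successive annual interim reports could therefore show a rising rate even if the underlying hazard were constant.

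**Working it through.** **The plan's own figures.** The protocol states no number for the person-time rate. Its sample-size figures (Section 8.5) reproduce: −ln(0.05)/0.001 = 2995.7, or about 3000 patients. The Clopper-Pearson limits for 3, 15 and 30 events in 3000 come out at 0.02–0.29%, 0.28–0.82% and 0.68–1.42%, as in Table 2. These are proportions of patients and do not use exposure time, so this point does not touch them.

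**General result.** Let E be all events during observation.

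- Rate as written = E / PY_exposed
- Matched whole-observation rate = E / PY_observed
- Ratio = PY_observed / PY_exposed

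This ratio exceeds 1 as soon as any patient stops ocrelizumab and stays under observation. It needs no assumption about the hazard after stopping. Compared with an on-treatment rate, the ratio is 1 + E_off/E_on, which exceeds 1 once any off-treatment event occurs.

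**Inputs for the size.**

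- From the protocol: 3000 patients; 30-month recruitment; observation of 7.5 to 10 years.
- Assumed: uniform accrual, so mean observation is 8.75 years and PY_observed = 3000 × 8.75 = 26,250; no loss to follow-up; constant discontinuation hazard m of 0.02, 0.05 or 0.10 per year; no restarts.

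Mean exposure for observation length T is (1 − e^(−mT))/m. Averaged over T uniform on 7.5 to 10, it is (1/m) × [1 − (e^(−7.5m) − e^(−10m))/(2.5m)]. For m = 0.05: 20 × [1 − (0.68729 − 0.60653)/0.125] = 7.08 years.

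| Assumed m | Mean exposure (years) | PY_exposed | Ratio | A matched 0.40 per 100 PY would appear as |
|---|---|---|---|---|
| 0.02 | 8.023 | 24,068 | 1.09 | 0.44 |
| 0.05 | 7.079 | 21,236 | 1.24 | 0.49 |
| 0.10 | 5.821 | 17,462 | 1.50 | 0.60 |

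The 0.40 is the pooled first-neoplasm rate in Section 6.2, used here only as an illustrative level.

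**Sensitivity.**

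- Reading 10% as an annual probability (hazard −ln 0.9), with everyone followed for 8.75 years, gives 1.53 instead of 1.50.
- On that same basis, counting exposure to 6 months after the last dose lowers the factor from 1.24 to 1.21 at 5% and from 1.53 to 1.46 at 10%. A lag in the denominator alone shrinks the mismatch but does not remove it.
- Suppose the hazard is 0.40 per 100 PY on treatment and half that afterwards, with m = 0.10. Events are 0.004 × 17,462 + 0.002 × 8,788 = 87.4. The rate as written is 87.4/17,462 = 0.50 per 100 PY. The on-treatment rate is 0.40 and the whole-observation rate is 87.4/26,250 = 0.33.

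**Time course.** With one year of follow-up for everyone, the ratio is 0.05/(1 − e^(−0.05)) = 1.03 for m = 0.05 and 0.10/(1 − e^(−0.10)) = 1.05 for m = 0.10. At five years with m = 0.05 it is 0.25/(1 − e^(−0.25)) = 1.13.

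**The case against.** The strongest objection is that the numerator is inferred. The rate sentence fixes only a denominator. The reference to all reported events is in the sentence before it and describes the safety analysis generally, and Section 10.1.2.1 is a collection rule. An exposure-based rate limited to on-treatment events would also fit the rate sentence. On-treatment windows and lags are ordinary SAP content, and the protocol defers detail to the SAP. This stands to the extent that one cannot say the sponsor intends the mismatch. It does not dispose of the point: the protocol commits to an exposure denominator, describes the analysed events without restriction, and sets a treatment-linked window only for pregnancies. A SAP that follows this wording inherits the problem.

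A reader might also infer three stronger things that the protocol does not support.

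- *That this is the only safety measure adjusted for follow-up.* The separate sentence on time-adjusted analyses may mean total observed time, or may be the same analysis mentioned twice. The protocol does not say.
- *That the distorted rate goes into the two global safety studies.* Sections 3 and 8.1 say that the data are included, not this summary rate.
- *That it will be compared with 0.40 per 100 patient-years.* That figure is background, and no such comparison is planned.

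It is also true that all analyses are exploratory, and that the events and dates are collected either way, so no information is lost.

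**Conclusion.** The point holds as a mismatch in the wording of Section 8.7.1. Followed literally, off-treatment events enter the numerator and off-treatment time is left out of the denominator, so the rate is biased upward relative to the matched whole-observation rate. The direction follows once any patient stops and remains under observation. The size cannot be taken from the protocol. Under assumed discontinuation of 2%, 5% or 10% per year, uniform accrual and no loss to follow-up, it is about 1.1-, 1.2- or 1.5-fold at the end of the study. At one year it is about 1.03 to 1.05 for 5% to 10%.

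It would go too far to state as fact that the reported malignancy, infection and death rates will be inflated by these amounts. The numerator is read from adjacent text, exposure is undefined, and the discontinuation rates are assumptions. The primary Clopper-Pearson proportions and the sample size are not in question.

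**What to change.** In Section 8.7.1, state that the numerator and denominator of every patient-year rate cover the same window, and replace the single exposure-based rate with two:

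1. **Whole observation:** all events from enrolment to end of observation, over total observed patient-years. This is needed especially for malignancies, malignancy mortality and death.
2. **On treatment:** only events during treatment plus a lag window set in the SAP, over patient-years in exactly that window.

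For rates of a first malignancy, end each patient's time at the first event. State also which time the sentence on time-adjusted analyses refers to, or merge it with these rates.

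The cost is a paragraph of text and one extra set of tables. No new data are needed, because start, stop and restart dates of ocrelizumab are already collected (Section 8.4.2 and Table 1). Some rates will be lower than under the current wording.
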